12.1.3. Progression-free survival

Progression-free survival (PFS) is defined as the time (in months) from the date of first intake of SL-901 to the date of the first documentation of PD (per RECIST v1.1) or death due to any cause, whichever occurs first, regardless of whether the patients withdraws from study treatment.

PFS will be analyzed by cohort and overall using the Kaplan-Meier method, with the median, 25th and 75th percentiles as well as PFS rates at 3, 6 and 12 months (and every 6 months thereafter until the end of follow-up or no more subjects are at risk) reported along with the 2-sided 95% CIs calculated according to Brookmeyer and Crowley using a linear transformation (CONFTYPE=LINEAR in SAS Proc LIFETEST). Number and percentage of patients with each event type (PD or death) and censoring reasons will be presented by cohort.

PFS will be displayed graphically using Kaplan-Meier curves.

These analyses will be presented by cohort both in the Efficacy and in the Per Protocol populations.

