7.4.2. Protocol Deviations and Data Review Meeting

Critical, Major or minor protocol deviations are defined based on the impact on the efficacy or safety of study treatments.

Before database lock, a data review meeting (DRM) will take place to identify protocol deviations. Major protocol violations will be discussed, and on a case-by-case basis it will be determined whether or not to exclude the patients from the Per Protocol population. The final decisions on which patients to include or exclude from the Per Protocol population will be finalized prior to database lock.

Categories of protocol violations will be defined and will be integrated in the statistical analysis.

Significant protocol violations that potentially compromise the data integrity and patients' safety will be summarized on the Safety Population as follows:

- The number and percentage of patients with a critical protocol deviation by cohort and overall and by type of deviation
- The number and percentage of patients with a major protocol deviation by cohort and overall and by type of deviation
- The number and percentage of patients with a minor protocol deviation by cohort and overall and by type of deviation
 - A by-patient listing of all critical protocol deviations.
 - A by-patient listing of all major protocol deviations.
 - A by-patient listing of all minor protocol deviations.

8. Determination of sample size

No formal sample size calculation is required in this Phase 1 dose-escalation and dose expansion study. For each dosing schedule, 3 to 6 patients are to be enrolled in each dose escalation cohort in Part 1a. Up to 60 patients in total are to be enrolled in the dose escalation cohorts.

The total number of patients to be enrolled is dependent upon the observed safety profile, which will determine the number of patients per dose cohort, as well as the number of dose-escalations required to achieve the MTD.

A sample size of at least 3 patients in each cohort, expanding to 6 patients in the event of a marginal DLT rate (33%), is a conventional approach in dose-escalation studies of investigational oncologic agents.

Six to 12 patients in each expansion cohort (up to 4 cohorts) are to be enrolled in Part 1b.

9. Randomization Methodology

Not applicable.

10. Stopping Rules and Blinding

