12.1.2. Duration of Response

Duration of response (DOR) is defined, for patients with OR, as the time (in months) from the first documentation of objective response (CR or PR) to the date of first documentation of PD.

Duration of Complete Response (DOCR) is defined, for patients with a confirmed BOR of CR, as the time from the first documentation of CR to the date of first documentation of PD.

DOR and DOCR will be calculated as follows:

$$\text{DOR (months)} = [\text{date of event or censoring} - \text{first date of OR} + 1] / 30.4375$$

$$\text{DOCR (months)} = [\text{date of event or censoring} - \text{first date of CR} + 1] / 30.4375$$

DOR and DOCR will be censored at the last tumor assessment if the patient did not have disease progression. If a patient receives a new systemic anti-cancer therapy before disease progression, DOR and DOCR will be censored at the last tumor assessment before the date of initiation of new systemic anti-cancer therapy. In addition, patients who experience PD after ≥ 2 missing tumor assessments will be censored at the last tumor assessments prior to the missed visits.

[figure not shown]
DOR and DOCR will be analyzed by cohort using the Kaplan-Meier method, with the median, 25th and 75th percentiles as well as DOR and DOCR rates at 3, 6 and 12 months (and every 6 months thereafter until the end of follow-up or no more subjects are at risk) reported along with the 2-sided 95% CIs calculated according to Brookmeyer and Crowley using a linear transformation (CONFTYPE=LINEAR in SAS Proc LIFETEST). Number and percentage of patients with event (PD) and censoring reasons will be presented by cohort.

[figure not shown]
DOR and DOCR will be displayed graphically using Kaplan-Meier curves.

These analyses will be presented by cohort both in the Efficacy and in the Per Protocol populations.

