12.1.4. Overall Survival

Overall survival (OS) is defined as the time from the date of first SL-901 intake to the date of death due to any cause, regardless of whether the patient withdraws from study treatment or receives another anticancer therapy.

OS (months) = [date of death or censoring – date of first SL-901 intake +1]/30.4375

Patients not known to have died at the time of analysis will be censored at the last recorded date on which the subject was known to be alive, based on the data collected in the “Long Term Follow-up” eCRF.

OS will be analyzed by cohort and overall using the Kaplan-Meier method, with the median, 25th and 75th percentiles as well as OS rates at 12, 18 and 24 months (and every 6 months thereafter until the end of follow-up or no more subjects are at risk) reported along with the 2-sided 95% CIs calculated according to Brookmeyer and Crowley using a linear transformation (CONFTYPE=LINEAR in SAS Proc LIFETEST). Number and percentage of patients with event (death) and censored will be presented by cohort and overall.

[figure not shown]
OS will be displayed graphically using Kaplan-Meier curves.

[figure not shown]
These analyses will be presented by cohort both in the Efficacy and in the Per Protocol populations.

[figure not shown]

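### Linear-scale Kaplan-Meier intervals give out-of-range landmark limits in cohorts of 3 to 6 and under-cover at n = 6 and 12; log-log is a cheap partial repair

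*SAP*

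**What the plan says.** SAP 12.1.3 states that "PFS will be analyzed by cohort and overall using the Kaplan-Meier method". The quantities to be reported are the three quartile times and the landmark rates, starting at 3, 6 and 12 months. Each gets a two-sided 95% interval of the Brookmeyer-Crowley type, computed "using a linear transformation (CONFTYPE=LINEAR in SAS Proc LIFETEST"). SAP 12.1.4 applies the same method to OS ("OS will be analyzed by cohort and overall using the Kaplan-Meier method"), with different landmark months. SAP 12.1.2 does so for the two duration endpoints ("DOR and DOCR will be analyzed by cohort using the Kaplan-Meier method"), which include responders only.

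On size, SAP section 8 says: "For each dosing schedule, 3 to 6 patients are to be enrolled in each dose escalation cohort in Part 1a". The pooled ceiling is in the same section: "Up to 60 patients in total are to be enrolled in the dose escalation cohorts". SAP section 4 records that the study stopped early and that Part 1b never opened, so no expansion cohorts add larger groups.

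The SAP gives no reason for the linear scale. It has no rule for limits outside 0 to 100%, none for an estimate of exactly 0% or 100%, and no minimum number at risk. For ORR, DCR and CRR in the same cohorts, SAP 12.1.1 uses exact Clopper-Pearson limits.

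**The concern.** On the linear scale the interval for a survival rate is the estimate plus or minus 1.96 Greenwood standard errors. With no censoring before the landmark this is the Wald interval for a binomial proportion, which is known to behave badly in small samples. The same SAP avoids it for the response rates by using exact limits.

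These are the only intervals on the time-to-event activity endpoints. A reader of the report would take them as 95% limits. If real coverage is far lower, or limits fall where no rate can lie, the precision of the activity data is misdescribed.

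**Working it through.** **Inputs.** Two-sided 95%, z = 1.960, linear scale (SAP 12.1.2 to 12.1.4). Cohort n = 3 to 6 per schedule, pooled n up to 60 (SAP section 8). I add n = 12 because five cohort numbers in SAP Table 1 carry both a QD and a BID arm. The SAP does not say whether these share a column; if they do, 6 + 6 = 12. Replaced patients also stay in the Efficacy population (SAP 7.3), so a cohort can exceed 6.

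**Assumptions.** The documents give no true survival rate S, so I use S = 0.25, 0.50 and 0.75, with 0.9 as an extreme. The main calculation has no censoring before the landmark. I read the linear option as applying to landmark rates as well as quantiles. An estimate of 0% or 100% has zero standard error and is counted as a miss.

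**Formulas.** With x of n patients event-free, Ŝ = x/n.
- Linear: Ŝ ± 1.96 √(Ŝ(1−Ŝ)/n).
- Log-log: Ŝ^exp(±1.96 s), with s = √((1−Ŝ)/(nŜ)) / |ln Ŝ|.
- Coverage: the sum of binomial probabilities over those x whose interval contains S.

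**Single intervals.**
- 5 of 6 event-free, linear: SE = √(0.8333 × 0.1667/6) = 0.152, giving 53.5% to 113.2%. Log-log: s = 1.001, giving 27.3% to 97.5%.
- 1 of 3 event-free, linear: −20.0% to 86.7%.

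**Coverage at n = 6, S = 0.5.** Linear limits contain 0.5 only for x = 2, 3, 4: (15 + 20 + 15)/64 = 78.1%. Log-log limits contain it for x = 1 to 5: 62/64 = 96.9%. Limits leave 0 to 100% for x = 1, 2, 4, 5: 42 of the 62 non-degenerate outcomes, or 68%.

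**Landmark rates at S = 0.25 / 0.50 / 0.75 (%).**

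| n | Linear coverage | Log-log coverage | Zero-width interval | Out of range, given not zero-width (linear) |
|---|---|---|---|---|
| 3 | 56.3 / 75.0 / 56.3 | 56.3 / 75.0 / 56.3 | 44 / 25 / 44 | 100 / 100 / 100 |
| 4 | 63.3 / 87.5 / 63.3 | 68.0 / 87.5 / 63.3 | 32 / 13 / 32 | 69 / 57 / 69 |
| 5 | 74.7 / 93.8 / 74.7 | 76.2 / 93.8 / 74.7 | 24 / 6 / 24 | 100 / 100 / 100 |
| 6 | 78.4 / 78.1 / 78.4 | 81.7 / 96.9 / 78.4 | 18 / 3 / 18 | 84 / 68 / 84 |
| 12 | 82.7 / 85.4 / 82.7 | 95.4 / 97.8 / 91.4 | 3 / 0 / 3 | 37 / 4 / 37 |

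At n = 3 to 5 the zero-width column accounts for most or all of the gap to 100%, and the two scales are nearly the same. At S = 0.9 log-log is lower: 32.8% against 40.1% at n = 5, and 45.3% against 46.7% at n = 6.

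**Median (Brookmeyer-Crowley).** At n = 3, 4 and 5 both scales give 75.0%, 87.5% and 93.8%. At n = 6 linear gives 78.1% and log-log 96.9%. If an unbounded upper limit is reported as not estimable, n = 3 to 5 rise to 87.5%, 93.8% and 96.9% on both scales, but linear at n = 6 stays at 78.1%.

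**Pooled.** At S = 0.5, n = 24 and 36 give about 93.6% linear and 95.5% log-log; n = 60 gives 94.8% and 96.0%.

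**With censoring.** I simulated 20,000 replicates with independent censoring at a hazard that gives 20% by the landmark. At n = 6 and S = 0.3 / 0.5 / 0.7, linear covers 80.8 / 82.3 / 82.4% and log-log 82.9 / 94.1 / 79.3%.

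**The case against.** The strongest reply is that the linear scale is not the main fault at the cohort sizes in question. Leaving out estimates of 0% or 100%, linear coverage at S = 0.25, 0.50 and 0.75 is 100/100/100% at n = 3, 93/100/93% at n = 4 and 98/100/98% at n = 5. Only n = 6 at S = 0.5 is clearly deficient, at 81%. That stands. A reader might infer that the scale causes all the under-coverage in cohorts of 3 to 6, or that log-log would restore 95%. The calculation supports neither.

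A reader might also infer that the quantile intervals go out of range. They do not: their limits are times. Nor do the documents show that impossible values would be printed, since they are silent on truncation. Truncation would hide such limits without changing coverage.

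The method is also prespecified and consistent across three sections, the endpoints are descriptive, and individual times are already listed (Listings 16.2.6.4 to 16.2.6.7). These facts limit the consequence. They do not justify a scale that does worse at n = 6 and 12 for mid-range rates when the alternative costs one option.

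**Conclusion.** The point holds in limited form. At cohort size the linear scale puts most non-degenerate landmark-rate intervals partly outside 0 to 100% before any truncation. It costs real coverage at n = 6 near S = 0.5 (78% against 97%, for both the landmark rate and the median) and at n = 12 for S of 0.25 to 0.75 (83 to 85% against 91 to 98%). At n = 3 to 5 the labelled 95% is not reached on either scale, mainly because of zero-width intervals. For pooled PFS and OS at n = 24 to 60 the difference is about 0 to 2 points at mid-range rates; the actual pooled N is not stated.

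The coverage figures rest on assumed true rates, no censoring before the landmark except in the simulation, and counting zero-width intervals as misses. The matter is accuracy of reporting for descriptive secondary endpoints. Escalation and the MTD rest on DLTs, so no dose decision depends on it.

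**What to change.** - In SAP 12.1.2, 12.1.3 and 12.1.4, replace CONFTYPE=LINEAR with CONFTYPE=LOGLOG for quantile and landmark-rate intervals.
- Add a rule for estimates of 0% or 100%: report the interval as not estimable or, where nobody is censored before the landmark, give the exact binomial interval already used in SAP 12.1.1.
- For cohorts of 3 to 5, rely on the listed individual times rather than on Kaplan-Meier intervals.

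The cost is one program option, one phrase in three sections and a short added rule, with no new data. The downside is that lower limits for high estimates drop (27.3% instead of 53.5% for 5 of 6), and coverage is slightly lower at extreme rates in some small cohorts.

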12.1.4. Overall Survival

Overall survival (OS) is defined as the time from the date of first SL-901 intake to the date of death due to any cause, regardless of whether the patient withdraws from study treatment or receives another anticancer therapy.

OS (months) = [date of death or censoring – date of first SL-901 intake +1]/30.4375

Patients not known to have died at the time of analysis will be censored at the last recorded date on which the subject was known to be alive, based on the data collected in the “Long Term Follow-up” eCRF.

OS will be analyzed by cohort and overall using the Kaplan-Meier method, with the median, 25th and 75th percentiles as well as OS rates at 12, 18 and 24 months (and every 6 months thereafter until the end of follow-up or no more subjects are at risk) reported along with the 2-sided 95% CIs calculated according to Brookmeyer and Crowley using a linear transformation (CONFTYPE=LINEAR in SAS Proc LIFETEST). Number and percentage of patients with event (death) and censored will be presented by cohort and overall.

[figure not shown]
OS will be displayed graphically using Kaplan-Meier curves.

[figure not shown]
These analyses will be presented by cohort both in the Efficacy and in the Per Protocol populations.

[figure not shown]
12.2. Subgroup analyses

Not Applicable.

12.3. Pharmacokinetic analysis

13. Tables, listings and figures

13.1. Statistical Analysis Report

The TLF (Tables, Listings and Figures) will follow the list of tables, plots, and listings agreed with the Study Team.

13.2. Index of TLFs

13.2.1. Tables

[Table 14.1.1.1: Analysis Populations](#)

[Table 14.1.1.2: Patient Disposition](#)

[Table 14.1.1.3: Critical Protocol Deviations](#)

[Table 14.1.1.4: Major Protocol Deviations](#)

[Table 14.1.1.5: Minor Protocol Deviations](#)

[Table 14.1.2.1: Demographic Characteristics](#)

[Table 14.1.2.2: Tumor History](#)

[Table 14.1.2.3: Tumor Mutational Status](#)

[Table 14.1.2.4: Medical History by SOC and PT](#)

[Table 14.1.2.5: Concomitant Medical Conditions by SOC and PT](#)

[Table 14.1.3.1: Prior Medications by ATC Code](#)

[Table 14.1.3.2: Concomitant Medications by ATC Code](#)

[Table 14.1.3.3: Prior and Concomitant Medications by ATC Code](#)

[Table 14.1.3.4: Overview of Prior Cancer Drug Therapies](#)

[Table 14.1.3.5: Prior Cancer Drug Therapies by ATC code](#)

[Table 14.1.3.6: Prior Cancer Radiotherapies](#)

[Table 14.1.3.7: Prior Procedures by SOC and PT](#)

[Table 14.1.3.8: Concomitant Procedures by SOC and PT](#)

[Table 14.1.3.9: Treatment Exposure](#)

[Table 14.3.1.1.1: Summary of Treatment-Emergent Adverse Events](#)

[Table 14.3.1.1.2: DLTs by SOC and PT](#)

[Table 14.3.1.1.3: TEAEs by SOC and PT](#)

[Table 14.3.1.1.4: TEAEs by Maximum CTCAE Grade, SOC and PT](#)

[Table 14.3.1.1.5: TEAEs Leading to Interruption of Study Treatment by SOC and PT](#)

[Table 14.3.1.1.6: TEAEs Leading to Withdrawal of Study Treatment by SOC and PT](#)

[Table 14.3.1.1.7: TEAEs Leading to Dose Reduction of Study Treatment by SOC and PT](#)

[Table 14.3.1.1.8: TEAEs Leading to Death by SOC and PT](#)

[Table 14.3.1.2.1: SAEs by SOC and PT](#)

[Table 14.3.1.2.2: SAEs by Maximum CTCAE Grade, SOC and PT](#)

[Table 14.3.1.3.1: TEAEs Related to Study Treatment by SOC and PT](#)

[Table 14.3.1.3.2: TEAEs Related to Study Treatment by Maximum CTCAE Grade, SOC and PT](#)

[Table 14.3.1.3.3: Treatment-related TEAEs Leading to Interruption of Study Treatment by SOC and PT](#)

[Table 14.3.1.3.4: Treatment-related TEAEs Leading to Withdrawal of Study Treatment by SOC and PT](#)

[Table 14.3.1.3.5: Treatment-Related TEAEs Leading to Dose Reduction of Study Treatment by SOC and PT](#)

[Table 14.3.1.3.6: Treatment-Related TEAEs Leading to Death by SOC and PT](#)

[Table 14.3.1.4.1: Serious Treatment-related TEAEs by SOC and PT](#)

[Table 14.3.1.4.2: Serious Treatment-related TEAEs by Maximum CTCAE Grade, SOC and PT](#)

[Table 14.3.5.1: 12-Lead ECG by Visit](#)

[Table 14.3.5.2: Categorical Analysis of 12-lead ECG](#)

[Table 14.3.5.3: Hematology by Visit](#)

[Table 14.3.5.4: Blood Chemistry by Visit](#)

[Table 14.3.5.5: Coagulation by Visit](#)

[Table 14.3.5.6: Hematology – Shift to Worst Post-Baseline Category](#)

[Table 14.3.5.7: Blood Chemistry – Shift to Worst Post-Baseline Category](#)

[Table 14.3.5.8: Coagulation – Shift to Worst Post-Baseline Category](#)

[Table 14.3.5.9: ECOG Performance Status](#)

[Table 14.3.5.10: ECOG Performance Status – Shift to Worst Post-Baseline Value](#)

Table 14.3.5.11: Echocardiogram**Table 14.2.1: Best Overall Response and Objective Response – Investigator's Assessment (RECIST v1.1)****Table 14.2.2: Duration of Response - Investigator's Assessment (RECIST v1.1)****Table 14.2.4: Duration of Complete Response - Investigator's Assessment (RECIST v1.1)****Table 14.2.6: Progression-free Survival - Investigator's Assessment (RECIST v1.1)****Table 14.2.8: Overall Survival - Investigator's Assessment (RECIST v1.1)****Table 14.4.1: SL-901 Plasma PK Concentrations by Cohort, Visit and Nominal Time****Table 14.4.8: SL-901 Plasma PK Parameters by Cohort and Visit**

13.2.2. Listings

Listing 16.2.1.1: Patient Disposition**Listing 16.2.1.2: Analysis Populations****Listing 16.2.2.1: Critical Protocol Deviations****Listing 16.2.2.2: Major Protocol Deviations****Listing 16.2.2.3: Minor Protocol Deviations****Listing 16.2.4.1: Demographic Characteristics****Listing 16.2.4.2: Tumor History****Listing 16.2.4.3: Tumor Mutation Characteristics****Listing 16.2.4.4: Medical History****Listing 16.2.4.5: Prior Cancer Drug Therapies****Listing 16.2.4.6: Prior Procedures****Listing 16.2.4.7: Prior Radiotherapies****Listing 16.2.4.8: Prior and Concomitant Medications****Listing 16.2.4.9: Procedures****Listing 16.2.4.10: Tumor Biopsy****Listing 16.2.5.1: Treatment Administration****Listing 16.2.5.2: Drug Accountability****Listing 16.2.7.1: Adverse Events****Listing 16.2.7.2: Treatment-Emergent Adverse Events****Listing 16.2.7.3: Dose-Limiting Toxicities****Listing 16.2.7.4: Treatment-Related Treatment-Emergent Adverse Events****Listing 16.2.7.5: Serious Treatment-Emergent Adverse Events****Listing 16.2.7.6: Serious Treatment-Related Treatment-Emergent Adverse Events****Listing 16.2.8.1: Vital Signs****Listing 16.2.8.2: Physical Examination****Listing 16.2.8.3: 12-Lead ECG****Listing 16.2.8.4: Echocardiogram****Listing 16.2.8.5: Hematology****Listing 16.2.8.6: Blood Chemistry****Listing 16.2.8.7: Coagulation****Listing 16.2.8.8: ECOG Performance Status****Listing 16.2.8.9: Reproductive Status****Listing 16.2.6.1: Tumor Lesions – Investigator's Assessment (RECIST v1.1)****Listing 16.2.6.2: Tumor Response – Investigator's Assessment (RECIST v1.1)****Listing 16.2.6.3: Long-Term Follow-Up Survival Status****Listing 16.2.6.4: Duration of Response (DOR) – Investigator's Assessment****Listing 16.2.6.5: Duration of Complete Response (DOCR) – Investigator's Assessment****Listing 16.2.6.6: Progression Free Survival (PFS) – Investigator's Assessment****Listing 16.2.6.7: Overall Survival (OS)****Listing 16.2.9.1: PK Plasma Concentrations****Listing 16.2.9.2: PK Plasma Parameters**

[Listing 16.2.9.3: PD Sampling](#)

13.2.3. Figures

[Figure 14.2.3: Kaplan-Meier Plot of Duration of Response – Investigator's assessment \(RECIST v1.1\)](#)
[Figure 14.2.5: Kaplan-Meier Plot of Duration of Complete Response – Investigator's assessment \(RECIST v1.1\)](#)
[Figure 14.2.7: Kaplan-Meier Plot of Progression-free Survival – Investigator's assessment \(RECIST v1.1\)](#)
[Figure 14.2.9: Kaplan-Meier Plot of Overall Survival – Investigator's assessment \(RECIST v1.1\)](#)
[Figure 14.4.2: SL-901 Individual Steady-State Plasma Concentration-time Curves – Linear Scale](#)
[Figure 14.4.3: SL-901 Individual Steady-State Plasma Concentration-time Curves – Semi-Log Scale](#)
[Figure 14.4.4: SL-901 Mean \(\$\pm\$ SD\) Plasma Concentration-time Curves – Run-In – Linear Scale](#)
[Figure 14.4.5: SL-901 Mean \(\$\pm\$ SD\) Plasma Concentration-time Curves – Cycle 1 Day 15 – Linear Scale](#)
[Figure 14.4.6: SL-901 Mean \(\$\pm\$ SD\) Plasma Concentration-time Curves – Run-In - Semi-Log Scale](#)
[Figure 14.4.7: SL-901 Mean \(\$\pm\$ SD\) Plasma Concentration-time Curves – Cycle 1 Day 15 - Semi-Log Scale](#)
